Study Population:	Individuals 14 years and older, assigned female sex at birth, who are seeking care at a UPMC Magee-Womens Hospital (MWH) participating PAT study office complaining of symptoms of vaginitis
Study Duration:	Approximately two weeks of follow-up per participant with a projected accrual period of approximately 12 months
Study Sites:	Obstetric/gynecologic (OB/GYN) practices/offices located within UPMC Magee-Womens Hospital (MWH) and outpatient centers affiliated with the Department of OB/GYN or MWH
Study Design:	Two arm, randomized, single center trial of usual care vs. Xpert® Xpress MVP (multiplex vaginal panel; Cepheid, Sunnyvale, CA) directed care for vaginitis diagnosis and treatment

Individuals who are complaining of vaginitis symptoms and are seeking care at one of the PAT study participating offices/departments within or affiliated with MWH will be invited to participate. In this study, the office visit will serve as the enrollment (index) visit. Following informed consent, participants will complete a brief questionnaire and self-collect three vaginal swabs for three tests that are FDA-cleared for vaginitis diagnosis: Xpert® Xpress MVP, BD MAX™ Vaginal Panel (Becton-Dickinson, Franklin Lakes, NJ), and BD Affirm™ VPIII Microbial Identification Test (Affirm™ VPIII; Becton-Dickinson). Participants will be randomized (1:1) into one of two arms after collecting swabs.

In Arm 1, vaginitis diagnosis and treatment will be based on usual provider evaluation and treatment during the office visit. The Xpert® Xpress MVP test will be batched with delayed results made available to the provider following the participant's 2-week study follow-up telephone contact.

In Arm 2, the Xpert® Xpress MVP test will be run in real time as a point of care (POC) test at the time of the office visit and the results will be made available to the provider in approximately one hour. Providers will be asked to use the MVP test result for diagnosis and treatment of the participant.

All participants, regardless of arm, will complete a follow-up telephone contact approximately two weeks after their office/medical visit to assess symptom resolution and satisfaction.

The study will include review and collection of electronic medical record information related to the office/medical visit (i.e., evaluation, testing, diagnosis and treatment).

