1. To compare the proportion of study participants who are prescribed appropriate treatment at index visit or within 24 hours of index visit based on the provider assessment conducted at the time of the office/medical visit (Arm 1) to the proportion of study participants who are prescribed appropriate treatment when Xpert® Xpress MVP testing is performed and reported on the day of the office visit (Arm 2).
 - a. Appropriate treatment is defined as CDC recommended or FDA approved treatment based on diagnosis from the self-collected samples. A positive result from both FDA cleared molecular tests (Xpert® Xpress MVP; BD MAX™ Vaginal Panel) will be considered the gold standard for the diagnosis of vaginitis/vaginosis for data analysis.

2.2 Secondary Objectives:

1. To compare the accuracy of provider's diagnosis of vaginitis (usual care) to the diagnosis of vaginitis based on the results of the Xpert® Xpress MVP test at the office/medical visit.
2. To compare the proportion of women who experience resolution of vaginitis symptoms at the two week follow up contact after undergoing evaluation with a novel POC molecular test to the proportion of women with resolution of vaginitis symptoms after evaluation by their provider's usual care.
3. To evaluate participant satisfaction with usual care vs point of care testing for vaginitis. Questionnaires will be administered to all participants at the office visit and approximately two weeks after enrollment.
4. To compare the accuracy of a nonamplified probe-based platform (BD Affirm™ VPIII) that tests for *Candida*, *Trichomonas vaginalis* and *Gardnerella vaginalis* compared to the results of two FDA-cleared molecular tests for diagnosis of vaginitis/vaginosis: two NAAT platforms (Xpert® Xpress MVP; BD MAX™ Vaginal Panel).

2.3 Exploratory Objectives:

1. Assess the impact of vaginitis symptoms on patient quality of life and productivity through use of the Sheehan Disability Scale (SDS), which will be administered at enrollment. Results will be assessed overall and stratified by participant-reported severity based on the Patient Global Impression of Severity (PGIS) instrument.
2. To assess provider satisfaction/treatment confidence with usual care assessment vs Xpert® Xpress MVP testing through the Healthcare Provider Sub Study.

3. Study Population

The inclusion and exclusion criteria in this section will be utilized to ensure the appropriate selection of study participants.

3.1 Recruitment:

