- There is a potential for a breach of confidentiality to occur. There is a possibility for people other than the researchers involved in this study to gain access to the participant's research information. Extensive measures are taken to prevent this from occurring.

4. Study Procedures

Participants may be identified through pre-screening of schedules/electronic medical records and may be contacted/consented in advance of a scheduled appointment as permitted by the University of Pittsburgh Institutional Review Board (IRB). IRB approved flyers may also be used to recruit participants. Consent may be obtained by paper or electronically as approved by the IRB. If the patient is not reached or identified in advance of the visit, the patient may be approached at the time of their visit by study personnel. Following written/electronic informed consent, participants will be assigned a unique participant study number for the questionnaire and associated specimens.

After providing informed consent and confirming eligibility, the participant will be asked to complete a baseline questionnaire and collect vaginal specimens; the order of specimen

Cepheid Point of Care Evaluation of the Xpert® Xpress MVP

collection and questionnaire is not important and will depend largely on office flow. Questions will include demographics, current symptoms, recent relevant treatment in past 30 days, history of recurrent vaginitis in past 12 months, and baseline validated symptom score (PGIS) and the Sheehan Disability Scale (SDS).

Upon arrival for the office/medical visit, the participant will be provided instructions to self-collect vaginal swabs for the following three kits:

- Xpert® Swab Specimen Collection kit for the Xpert® Xpress MVP on the GeneXpert Xpress Instrument System
- BD Molecular Swab Collection kit for the BD MAX Vaginal Panel on the BD MAX™ System
- BD Affirm™ Ambient Temperature Transport System (ATTS) for the BD Affirm™ VPIII on the B-D MicroProbe® Processor.

Kits will be preassembled by researchers with the appropriate collection kits and swabs. Collection order of the swabs will be randomized to prevent collection bias. Patients/participants who are reached in advance of their office appointment (i.e. the day before or within 24 hours of the scheduled appointment) may be asked to come to the research clinic to complete research activities (i.e. informed consent, collection of swabs, completion of questionnaire).

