After swab collection, the participant will be randomly assigned to Arm 1 or Arm 2. The randomization will be assigned through REDCap. Participants will be made aware of which arm they were assigned to and will be handed a card to provide to their healthcare provider to make them aware they are in the PAT study and which arm they are assigned to (usual care vs. Xpert® Xpress MVP results). The card will also indicate what time the MVP results will be available (approximately one hour from the time of collection) for participants in Arm 2.

4.1 Arm 1:

For Arm 1 (usual care), the Xpert® Xpress MVP testing will be stored at room temperature and tested within 17 days of receiving the sample, as permitted, per manufacturer test instructions. The results of the MVP test will be entered into the electronic medical record as determined by the MWH Point of Care (POC) Committee AFTER the participant's two-week telephone contact. MVP test results will be available to the provider and participant through the EMR. The other two swab samples (BD Affirm™ ATTS and BD Molecular Swab Collection Kit) from participants in Arm 1 will be transported to the MWRI Lab for processing. The results of these tests are for research purposes only and will not be given to providers or entered into the medical record.

4.2 Arm 2:

For Arm 2, the Xpert® Xpress MVP test will be performed in real time (using the self-collected swab) in clinical areas at UPMC MWH by clinical non-laboratory research staff. GeneXpert Xpress Instrument Systems, provided by the sponsor, will be placed strategically in or near appropriate clinical space as determined by available space and in consultation with the hospital/office staff. The Xpert® Xpress MVP test takes approximately one hour to result.

Cepheid Point of Care Evaluation of the Xpert® Xpress MVP

Research staff will place the result the EMR once resulted. The other two swab samples (BD Affirm™ ATTS and BD Molecular Swab Collection Kit) from participants in Arm 2 will be transported to the MWRI Lab for processing. The results of these tests are for research purposes only and will not be given to providers or entered into the medical record.

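### The early research-clinic route permits randomisation and an Arm 2 result before the day of the office visit, which conflicts with the plan's own definition of Arm 2

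*Combined protocol and SAP*

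**What the plan says.** **Early route (section 4, Study Procedures).** Of patients whom staff contact ahead of time, the plan states: "i.e. the day before or within 24 hours of the scheduled appointment) may be asked to come to the research clinic". There they can sign consent, take their own swabs and fill in the questionnaire. The route is optional, and no expected share of participants is given.

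**Usual route (section 4).** "Upon arrival for the office/medical visit, the participant will be provided instructions to self-collect vaginal swabs for the following three kits".

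**Randomisation (section 4, before 4.1).** "After swab collection, the participant will be randomly assigned to Arm 1 or Arm 2". Next comes disclosure: "Participants will be made aware of which arm they were assigned to and will be handed a card to provide to their healthcare provider". For Arm 2 the card also gives the time of the result, put at about one hour after collection.

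**Arm 2 as defined elsewhere.** The synopsis (Study Design) says the MVP test "will be run in real time as a point of care (POC) test at the time of the office visit", and it makes the office visit the enrollment and index visit. The primary objective (2.1) concerns appropriate treatment "when Xpert® Xpress MVP testing is performed and reported on the day of the office visit (Arm 2"). The Schedule of Participant Study Visits and Evaluations puts consent, swabs, randomisation and the Arm 2 result in Visit 1, at time 0.

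**Endpoint (7.1, 7.2).** Appropriate treatment prescribed at the index visit or within 24 hours of it.

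**The concern.** On the usual route, swabs, randomisation, the MVP run and the provider's assessment all fall within one attendance. The early route can separate the first three from the last. Nothing in section 4 holds randomisation or the Arm 2 run until the office visit; both follow from collection, and collection may come earlier.

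Two things are at stake. The first is the intervention. An Arm 2 woman tested the day before has a result before her visit, and this is not the strategy set out in the synopsis and in 2.1. If some women take that path and others the usual one, the Arm 2 rate averages over two strategies, and the plan has no means of separating them.

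The second is loss after randomisation. A woman who already knows her arm, and in Arm 2 perhaps her result, may not attend. She would then be randomised without the index visit that defines her endpoint. The text of section 7 names no analysis population and gives no rule for her. Nor does it say whether a prescription issued on an early result before the office visit would count.

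**Working it through.** **1. The permitted sequence, step by step.**

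| Step | Source | When it may happen on the early route |
|---|---|---|
| Consent, swabs, questionnaire | Section 4, early-route sentence | Before the appointment; the day before is not excluded |
| Randomisation | Section 4, triggered by swab collection | Directly after collection |
| Arm disclosed, card handed over | Section 4 | Directly after randomisation |
| Arm 2 result | Section 4 (card); section 5 (given to the provider or entered in the EMR at once) | About one hour after collection |
| Office visit, as enrollment/index visit | Synopsis | Up to about a day later |
| Endpoint cut-off | 7.1 | 24 hours after the index visit |

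If collection is 24 hours before the visit and the window runs from the visit, collection to cut-off is 24 + 24 = about 48 hours. On the usual route it is about 24.

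**2. Comparison with the other statements.** A day-before run conflicts with the synopsis (time of the visit), 2.1 (day of the visit), the usual-route sentence in section 4 (swabs on arrival) and the schedule (Visit 1, time 0). A same-day stop some hours before the appointment satisfies 2.1 but sits uneasily with the synopsis and the usual-route sentence.

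**3. The plan's own figure.** Inputs from 7.1: 75% in usual care, a 15-point difference (so 90%), 150 per arm, two-sided Fisher's exact test at 0.05. Summing the probabilities of all 2×2 tables in which the test rejects gives power of 91.55%, against the stated 91%. It reproduces.

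**4. Power of a sensitivity analysis without early-route women.** The share s is an assumption. The number per arm is 150 × (1 − s), with the same test and rates.

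| s | Per arm | Power |
|---|---|---|
| 10% | 135 | 88.5% |
| 20% | 120 | 83.7% |
| 30% | 105 | 78.0% |

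**5. Direction of a mixed Arm 2 effect.** Take s = 30%; both gains are assumptions.
- If early-route Arm 2 women gained only half of the 15 points, the Arm 2 rate would be 0.75 + 0.15 × 0.7 + 0.075 × 0.3 = 87.75%, and power 77.6%.
- If a result in hand added 5 to 10 points, the Arm 2 rate would rise by 0.3 × 5 = 1.5 to 0.3 × 10 = 3.0 points.

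The documents do not favour either case.

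**6. Loss before the index visit.** Suppose 30% take the early route, and among them non-attendance is 10 points higher in one arm. The extra loss is 0.30 × 0.10 = 3% of that arm, or 0.03 × 150 = 4.5 women.
- Scored as failures: the shift is 3 points times the success rate they would have had. At 75% to 90% that is 2.25 to 2.7 points.
- Left out: the shift is the proportion lost times the outcome gap between leavers and stayers. With an assumed gap of 20 points it is 0.03 × 20 = 0.6 points.

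The sign depends on which arm loses more women and on how those women differ.

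**The case against.** The strongest reply is that the sequence is inferred. Grammatically, the 24-hour phrase says when the patient is reached, not when she attends the research clinic. The listed early activities include neither randomisation nor the MVP run. The synopsis, 2.1, 4.2 and the schedule all tie the test to the visit or to clinical areas, so staff might never randomise or test early. This stands to the extent that the text permits the sequence and does not prescribe it. It does not close the gap: swab collection is on the early list, section 4 makes it the trigger for what follows, and no sentence confines the early stop to the visit day.

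A reader might also infer three stronger conclusions, none of which the documents support.

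- **That part of Arm 2 does not receive same-day testing.** The route is optional, its share is not given, and a same-day early stop meets 2.1.
- **That the Arm 2 effect is overstated by some number of points.** Any such figure multiplies an assumed share by an assumed gain. A result one hour into the visit already falls well inside the 24-hour window, so an earlier result need not help. Section 4.2 offers waiting in the office, or leaving and being contacted, as examples of flexible practice; neither is the defined comparison.
- **That this route causes the arm to be known before the provider's assessment.** Disclosure before assessment is the open-label design for every participant. Only the longer lead time and the chance of non-attendance are specific to the route.

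**Conclusion.** The concern holds as a conflict within the plan. Section 4 permits women on the early route to be swabbed, randomised, told their arm and, in Arm 2, tested before the day of the office visit. That conflicts with the synopsis, 2.1, the usual-route sentence in section 4 and the schedule. It also opens an avoidable gap between randomisation and the index visit, in which women who know their arm can be lost.

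The share affected is not stated, and the size and direction of any bias are unknown. The shifts worked out above (0.6 to 3.0 points, against a 15-point target) and the power of 77.6% for a mixed Arm 2 illustrate assumed inputs and are not estimates. No figure in the plan is shown to be wrong. The change is still worth making: it is cheap, it matches the intervention to the stated objective, and it removes a source of loss after randomisation.

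**What to change.** Amend section 4 so that consent and questionnaire may be completed early, but REDCap randomisation takes place at check-in on the day of the office visit and the Arm 2 MVP run follows it that day. The simplest way is to limit swab collection to the visit day.

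If earlier collection is kept, first confirm against the manufacturer's instructions that Arm 2 tubes can be held. The 17-day allowance in 4.1 and section 5 is written for Arm 1.

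Record the times of collection, randomisation, check-in and result. State in section 7 how a randomised woman who does not attend the index visit is handled.

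If any woman was already randomised before her visit day, keep her in the primary analysis as randomised. Add a prespecified sensitivity analysis that excludes early-route women from both arms. The route is fixed at swab collection, before assignment, so excluding on it in both arms does not break the randomised comparison; the cost is the loss of power tabulated above.

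The change costs a short wording amendment, a REDCap timing check and a few time fields. The downside is some loss of scheduling convenience, and early-route Arm 2 women would no longer have a result waiting before the visit.

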5.1 Biohazard Containment

As the transmission of HIV and other blood-borne pathogens can occur through contact with biological specimens, appropriate blood and secretion precautions and training will be employed by all personnel in collection, handling and processing of all specimens for this study. Biohazardous waste will be contained according to institutional, and all other applicable regulations.

6. ASSESSMENT OF SAFETY AND CLINICAL MANAGEMENT

6.1 Risk Management

Participants will be encouraged to ask questions to ensure they understand the research study and procedures. No adverse events are expected to occur from collection of multiple vaginal swabs, therefore no adverse events will be collected for this study.

When feasible, electronic case report forms (eCRFs) will be the first point of data entry for this protocol and will also serve as the source documents.

This study will be conducted in compliance with the protocol and applicable regulatory requirements. All paper research charts are maintained in locked files in a locked room. The research staff, under the direction of the primary investigator, may create and maintain electronic logs on password-protected computers connected to the UPMC/Magee-Womens Research Institute network in the Reproductive Infectious Diseases research offices.

7. Biostatistical Data and Analysis

7.1 Sample size calculations

The primary endpoint is the proportion of study participants prescribed appropriate treatment at index visit or within 24 hours of index as defined by use of a CDC recommended treatment regimen and/or a treatment approved for that indication by the US FDA for vaginitis/vaginosis. A previous study found that 40% of women received inappropriate treatment for vaginitis in community practice settings (18). We anticipate a higher proportion of women are being treated appropriately at the proposed study site since UPMC MWH is a teaching hospital that specializes

in healthcare for women. For the present study, we are making the assumption that 75% of women will receive appropriate treatment in the standard of care arm. We hypothesize that women in the study arm in which study clinicians and patients are provided with same day access to Xpert® Xpress MVP will have a higher proportion of women receiving appropriate treatment. A sample size of 150 participants in each arm will have 91% power to detect a difference of at least 15 percentage points in each arm of the study based on a Fishers exact test evaluated at the 2-sided .05 significance level.

7.2 Primary Endpoint Analysis

The proportion of women prescribed appropriate treatment at index visit or within 24 hours of index between the two arms (usual care versus Xpert® Xpress MVP testing) will be assessed using Fisher's exact test.

7.3 Secondary and Exploratory Endpoint Analyses

Patient and Provider satisfaction with usual care versus point of care testing will be evaluated on a 5-point Likert scale with 1 being very satisfied to 5 being very dissatisfied. Responses will be dichotomized for analyses (very satisfied and satisfied versus all others). Differences in patient and provider satisfaction with and the proportion of women who experience resolution of vaginitis symptoms after treatment based on usual care and point of care testing will be evaluated using Fisher's exact test.

A positive result from both of the two FDA cleared molecular tests (Xpert® Xpress MVP; BD MAX™ Vaginal Panel) will be considered the gold standard for the diagnosis of vaginitis/vaginosis for analysis. Samples yielding discordant results will be retested using the reserve sample. Samples which are discordant after retesting will be evaluated separately.

Fisher's exact test will be used to compare the provider's diagnosis of vaginitis based on usual care to the diagnosis based on the results of point of care testing. The sensitivity, specificity, negative and positive predictive values of the BD Affirm™ VPIII test for *Candida*, *Trichomonas vaginalis* and *Gardnerella vaginalis* will be calculated and compared to those of the two FDA-cleared tests using the test for equality of proportions.

Patient quality of life and productivity will be assessed using the Sheehan Disability Scale (SDS) where 0 indicates no functional impairment and 30 high functional impairment. Descriptive statistics will be used to assess overall SDS scores. Differences in SDS scores by participant-reported severity will be evaluated using Kruskal-Wallis (continuous SDS score) and Fisher's exact (categorized SDS score) tests.

[figure not shown]
8. Costs and Payments:

The cost for the testing for vaginitis using the self-collected molecular methods will be covered by the study in both arms of the study. The cost of routine clinical care visits, which may include other diagnostic testing will not be covered by the study. Treatment may be prescribed by the healthcare provider according to usual care; the cost of this treatment will not be covered by the study.

Participants who complete the study will be compensated as approved by the University of Pittsburgh IRB. Participants may also be offered MWH garage parking passes for the office visit. Healthcare providers who participate in the sub study will be compensated for survey completion, as approved by the University of Pittsburgh IRB.

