The PAT study will also include a sub study to collect data from providers at UPMC MWH to better understand how providers feel about POC testing for vaginitis.

Prior to starting the PAT study, all providers from participating offices will be invited to complete a baseline survey that will include questions about current practices of diagnosing vaginitis, perceived need and interest in POC vaginitis testing, participant vs provider collected swabs, etc. The questionnaire will take approximately five minutes to complete, will be anonymous and will be done either by paper or directly through REDCap.

Following completion of the PAT study, providers who have had patients participate in the PAT study will be eligible to participate in the Healthcare Provider Sub Study. Interested providers will be invited to sign an informed consent and then will be provided with a (paper/electronic REDCap) survey to complete. The survey will include questions that are similar to the baseline questionnaire with additional questions regarding demographics (i.e. gender, age, practice years) their experience in the study, such as getting test results in the same day and confidence in accuracy of results.

Providers who cared for patients participating in the PAT Study are under no obligation to consent to the sub study. The risks of participating in the sub study are minimal and include inconvenience and breach of confidentiality. The data collected from providers will be entered into REDCap by provider type (i.e. MD, NP, PA, CNM) but not by provider name to protect the (provider) participant's confidentiality.

Providers who consent and complete the final survey will be compensated for their time, as approved by the IRB.

4.3.1 Inclusion Criteria:

1. Able and willing to provide informed consent
2. Provided clinical care to at least one PAT study participant on the date of their study enrollment
3. Willing to undergo all study-related assessments including answering questions/surveys

4.4 Electronic Medical Record Abstraction:

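### Cutting the 5-point satisfaction score to two levels probably costs power for patients, and the provider comparison applies an independent-groups test to overlapping clinicians whose surveys cannot be linked.

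*Combined protocol and SAP*

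**What the plan says.** Section 7.3 has patient and provider satisfaction "evaluated on a 5-point Likert scale with 1 being very satisfied to 5 being very dissatisfied". It then reduces the scale: "Responses will be dichotomized for analyses (very satisfied and satisfied versus all others". One method serves both groups, since differences between "usual care and point of care testing will be evaluated using Fisher's exact test". No ordinal analysis of satisfaction, and no paired or clustered one, is planned. The same section treats the Sheehan Disability Scale differently, with Kruskal-Wallis on the score and Fisher on its categories.

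Patient satisfaction is secondary objective 3 (Section 2.2). Provider satisfaction is exploratory objective 2 (Section 2.3).

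Section 4.3 describes two provider surveys:

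- **Baseline.** All providers at participating offices are invited before the study starts. The survey "will be anonymous and will be done either by paper or directly through REDCap".
- **Final.** It follows the study, repeats similar questions and adds new ones. Eligibility under Section 4.3.1 requires that the provider "Provided clinical care to at least one PAT study participant on the date of their study enrollment", in either arm.

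Provider data are stored by professional type and not by name. The documents do not say which survey carries the usual-care rating and which the point-of-care rating.

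**The concern.** There are two separate issues.

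**Patients.** The cut treats satisfied and very satisfied as the same answer. If most answers fall in those two categories, much of any difference between arms lies where the planned analysis cannot see it. A secondary objective could then end inconclusive although the collected data could have answered it.

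**Providers.** Fisher's exact test compares two independent groups. Here the final-survey respondents are a subset of the clinicians invited at baseline, and if both ratings sit on the final survey they come from the same people. Either way, the two sides of the comparison share clinicians. A contrast between the surveys also mixes change of opinion with change of respondents. Without a link, the pairing cannot be recovered after collection. Finally, a provider whose participants were all in Arm 1 would have no study experience of a same-day result, because Arm 1 results are released only after the two-week contact.

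**Working it through.** **The plan's own figure.** Section 7.1 states: "A sample size of 150 participants in each arm will have 91% power to detect a difference of at least 15 percentage points", "based on a Fishers exact test evaluated at the 2-sided .05 significance level". The control rate comes from "we are making the assumption that 75% of women will receive appropriate treatment in the standard of care arm", so the comparison is 75% with 90%. Summing the two binomial probabilities over all tables that Fisher's test rejects gives 91.6% power, so the figure reproduces. It concerns the primary endpoint; no power is stated for satisfaction.

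**Patients: inputs.** 150 per arm (Section 7.1). Two-sided 0.05, stated for the primary endpoint and assumed here. Usual-care shares of 40/33/15/8/4% from very satisfied to very dissatisfied, and a common odds ratio (OR) of 1.6 or 1.8, are assumptions.

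**Patients: proportional shift.** Each cumulative odds is multiplied by the OR. At the planned cut the usual-care share is 0.40 + 0.33 = 0.73, with odds 0.73/0.27 = 2.704.

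- OR 1.6: 4.326/5.326 = 0.812
- OR 1.8: 4.867/5.867 = 0.830

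Fisher's power is exact. Wilcoxon's is from 200,000 simulated trials with tie correction.

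| OR | Satisfied, usual care vs Arm 2 | Fisher on cut | Wilcoxon, five levels |
|---|---|---|---|
| 1.6 | 73% vs 81% | 35% | 59% |
| 1.8 | 73% vs 83% | 50% | 78% |

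Smaller simulations of the same setting gave about 34% to 49% against 60% to 77%, so these figures are good to a point or two.

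**Patients: other assumed distributions, OR 1.75, 150 per arm.**

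| Usual-care shares (%) | Satisfied | Fisher | Wilcoxon |
|---|---|---|---|
| 20/30/25/15/10 | 50% | 64% | 77% |
| 30/35/20/10/5 | 65% | 54% | 76% |
| 40/35/15/7/3 | 75% | 44% | 73% |
| 50/35/8/5/2 | 85% | 29% | 70% |
| 60/30/5/3/2 | 90% | 19% | 64% |

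Over ORs of 1.5 to 2.0 the loss runs from about 10 points (half satisfied) to 54 points (90% satisfied). Part of it is Fisher's conservatism and not the cut. In the 75% row an uncorrected z test on the same cut has 49%, so about 5 points come from the exact test and about 24 from the cut (73 − 49). With an assumed 15% loss to follow-up (128 per arm), the 85% row becomes 24% against 62%.

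**Patients: shifts that are not proportional** (from 40/35/15/7/3, 150 per arm).

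- 10 points move only from neutral to satisfied: Fisher 53%, Wilcoxon 12%.
- 15 points move only from satisfied to very satisfied: Fisher 4%, Wilcoxon 44%.

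**Providers: inputs.** No provider numbers or correlations are given. Assume that the same m = 50 clinicians rate both approaches, with 60% and 80% satisfied and within-provider correlation r.

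The variance of the difference is [p1(1−p1) + p2(1−p2) − 2c]/m, with c = r√[p1(1−p1)p2(1−p2)]. Treating the ratings as independent sets c = 0.

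- c = 0: SE = √(0.40/50) = 0.089
- r = 0.3: c = 0.3 × 0.196 = 0.059; SE = √(0.282/50) = 0.075
- r = 0.5: c = 0.098; SE = √(0.204/50) = 0.064

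The independence assumption therefore overstates the standard error. Simulated rejection rates:

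| r | Fisher, 60% vs 60% | Fisher, 60% vs 80% | Exact McNemar, 60% vs 80% |
|---|---|---|---|
| 0 | 3.3% | 52% | 50% |
| 0.3 | 1.2% | 51% | 66% |
| 0.5 | 0.3% | 52% | 82% |

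**Providers: exposure.** With 1:1 allocation, a provider with k participants has none in Arm 2 with probability 0.5^k: 50% for k = 1, 25% for k = 2, about 0.1% for k = 10. The documents give no distribution of k.

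**The case against.** A prespecified top-two proportion is easy to interpret, matches the proportion used for the primary endpoint and rules out choosing a cut point afterwards. The plan claims no power for satisfaction. All of that stands, and it is why the dichotomy should be kept as a supporting summary. The patient gain is also conditional: proportional odds favours Wilcoxon, and a change confined to the cut favours Fisher.

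Several stronger readings are tempting, but the documents do not support them.

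- *The patient comparison uses the wrong kind of test.* Participants are randomized 1:1, so their arms are independent. Only the loss of ordinal information, and a little from Fisher's conservatism, costs power.
- *The provider analysis risks false positives.* With positive correlation the error runs the other way.
- *Each provider is known to rate one approach per survey.* That is inferred. Section 4.3 lists current practice, perceived need and interest for the baseline, and names no satisfaction item. The final survey may already collect both ratings.
- *A paired test would change the conclusion.* This depends on the split. Take an assumed 30 clinicians with 18 and 25 satisfied: Fisher gives p = 0.084. Exact McNemar gives 0.039 with discordant pairs of 8 and 1, 0.065 with 9 and 2, and 0.092 with 10 and 3.
- *Some raters never receive an MVP result.* Arm 1 providers do receive one, but late. What they may lack is a same-day result. The 50% chance applies only to a provider with exactly one participant. At 300 participants over an assumed 30 clinicians, an average of 10 each, it is negligible.

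**Conclusion.** The point holds in a limited form.

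**Patients.** The independent-groups comparison is correct; the cut is the weakness. At 150 per arm, under the assumed shares and a proportional shift with OR 1.6 to 1.8, the planned analysis gives up about 24 to 28 points of power. The loss is larger when satisfaction is high. It rests on assumed distributions and reverses if change occurs only across the cut.

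**Providers.** The comparison is under-specified, and Fisher's independence assumption does not hold on either reading of Section 4.3. The consequence is lost power on an exploratory objective: 51% to 52% against 66% to 82% for 50 assumed pairs at correlation 0.3 to 0.5. A contrast between surveys also compares different sets of respondents. The missing link matters most because it cannot be repaired once the surveys are in.

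The primary analysis is unaffected.

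**What to change.** **Patients.** In Section 7.3, make a Wilcoxon rank-sum or proportional-odds comparison of the full score the main satisfaction analysis. Keep the prespecified dichotomy with Fisher's test as a supporting summary. This follows the pattern that Section 7.3 already uses for the Sheehan scale. Make the change before satisfaction data are seen by arm. It costs SAP wording, and some power if change occurs only across the cut.

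**Providers.** In Sections 4.3 and 7.3:

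1. State which survey supplies each rating.
2. Collect both the usual-care and the point-of-care rating on the final survey, or add a self-generated anonymous code to both surveys. If the baseline is already complete, only the first route remains.
3. Analyse pairs by McNemar's test (dichotomy) or Wilcoxon signed-rank (full score). Naming a paired test without step 2 fixes nothing; if pairs cannot be formed, report descriptively.
4. Report ratings of same-day testing for providers with at least one Arm 2 participant, which a single survey question can establish.

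The cost is SAP wording, a survey item or code with IRB notification, some unmatched codes and slightly fewer raters. Anonymity is preserved.
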